5.2 Adequacy of implementation of the intervention bundle

Measures of the adequacy of the implementation of the intervention bundle will be prepared including:

- pre-operative education
- receipt of a minimum number of PEEP titrations
- receipt of the planned recruitment maneuvers and PEEP titrations
- receipt of protocol defined neuromuscular blockade
- receipt of protocol defined neuromuscular blockade reversal
- used incentive spirometry consistent with the protocol
- adequate visits by the study coordinator each day (process measure)
- achievement of ambulation standards each day

5.3 Intraoperative Characteristics

A range of intraoperative characteristics will be used to describe the surgical course of the two groups, and the impact of the intervention bundle on intraoperative characteristics. These include:

- duration of surgery
- duration of mechanical ventilation
- multiple measures of the mechanical ventilation itself (e.g, tidal volume, PEEP, peak pressure, modified driving pressure (based on PEEP) and modified respiratory system compliance, etc.)
- heart rate
- mean arterial pressure
- fluids (crystalloids; colloids)
- blood loss
- vasoactive medications

6 General Analysis Considerations

6.1 Statistical Standards

6.1.1 Statistical Software

All analyses will be done in the latest version of SAS or R available at the Massachusetts General Hospital Biostatistics Center, the SDCC for the study.

6.1.2 Reporting Conventions

Given the planned sample size (375 participants per group), percent will be reported in whole numbers (no decimal places), rounded as needed.

For continuous variables, results will be reported to the same precision as the raw data. For derived variables, one decimal place will be used (two for the coefficient of variation of PEEP).

6.1.3 Summary Statistics

Summary statistics for categorical variables will be counts and percents. The percents for valid responses will be based on non-missing responses (e.g., if the variable has responses for Yes and No, the total of the two percents will be 100 even if some data is missing).

Summary statistics for continuous variables will be means and standard deviations.

6.1.4 General Analysis Approach

For the primary endpoint (the highest value on 5-Point PPC Grade, 0 to 4 through POD7), the Row Mean Score test from a Cochran-Mantel-Haenszel test stratified by site is used. Differences in the Row Mean Score and the associated 95% confidence limit are provided.

A Cochran-Mantel-Haenszel test (with site as a stratification variable) is used for binary variables. The relative risk and the associated 95% confidence limit will be provided.

A standard t-test is used for continuous variables and the difference between the groups and the associated 95% confidence will be provided. This approach provides results that are easier to understand than those using a difference estimate derived from a model adjusting for site, which would not be the same as the difference between the two observed means.

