4.1 Study Design

The PRIME-AIR trial is a prospective multicenter randomized controlled pragmatic trial with a blinded assessor. We studied 751 adult participants with moderate or high risk for PPCs undergoing elective major open abdominal surgery. Enrolled participants were randomized 1:1 to receive either the perioperative intervention (PRIME-AIR bundle) or control (usual care); randomization was stratified by site.

The overall aim for this specific analysis is to compare the number and severity of PPCs in patients receiving an individualized perioperative anesthesia-centered bundle to those receiving usual anesthetic care during open abdominal surgery as well as the secondary outcomes for the comparison between the two treatment groups.

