4.6 Sample Size

We estimated that 40% of participants in the control group would have pulmonary complications. If the bundle decreases the proportion of participants with complications by 35.29% (i.e, 25.88% would have complications in the intervention group compared to 40% in the control group), with no change in the distribution of the severity of complications, 750 participants (375 / treatment group), will provide 93% power to

detect the treatment effect as statistically significant (Cochran-Mantel-Haenszel test, row mean score test; $\alpha=0.05$, two-sided; based on simulations). The grant proposal contained a detailed discussion of the assumptions.

When the study was fully implemented the study team realized that approximately 6% of randomized participants would fail to be included in the study (revoking assent/consent on the day of surgery; no longer being a candidate for surgery; other reasons). The study team had not anticipated that this would occur. Therefore, we revised our plan to recruit approximately 795-800 participants to achieve 750 randomized participants having surgery with written consent.

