5.1 Baseline Characteristics

The following characteristics will be used to describe the participants in the study

- age, gender (female), race (White/Black/Asian/Other or more than one race), Hispanic, BMI
- comorbidities (active cancer; hypertension; GERD; diabetes)
- medications (statin use).
- total ARISCAT score on the day of surgery
- ASA Physical status
- hemoglobin
- preoperative O₂ saturation
- primary surgical organ classified as: gastric; pancreatic; hepatobiliary [combined]; colorectal [combined]; urological (kidney, bladder combined), and other
 - more than one organ is possible
 - “other” is used for surgery addressing topography other than those specified

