6.3 Covariates and Subgroups

The primary outcome measure (highest grade of PPC through POD 7) will be summarized for the following subgroups:

- gender (male; female)
- age (under 50; 50-80, over 80)
- BMI (under 18.5; 18.5-24.9; 25.0-29.9; 30-34.9)
- race (white / non-white)
- ethnicity (Hispanic / not Hispanic)
- duration of surgery (under 4 hours, 4-6 hours; > 6 hours)
- ASA physical status (I and II vs. III and IV)
- ARISCAT score (intermediate [26-44] vs high [45 or higher])
- Neuraxial intraoperative analgesia (Y/N)
- Neuromuscular blockade monitoring (quantitative vs qualitative/missing)
- Neuromuscular blockade reversal agent (Sugammadex vs Neostigmine)

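### The primary test adjusts for site only and leaves out the ARISCAT risk score, so the trial gives up a modest amount of precision and some protection against chance imbalance in risk

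*SAP*

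**What the plan says.** The protocol (Section VI, primary endpoints) and the SAP (6.1.4 and 8.1.1) name the same primary analysis. In SAP 6.1.4, "the Row Mean Score test from a Cochran-Mantel-Haenszel test stratified by site is used", and the difference in row mean score is reported with a 95% confidence interval. This matches the design, since "randomization was stratified by site" (SAP 4.1).

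ARISCAT has three roles in the documents:

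- **Entry.** A score of 26 or more is an inclusion criterion (Protocol Section III; SAP 4.4.1), and the protocol describes the score as validated for PPC risk.
- **Baseline description.** SAP 5.1 lists "total ARISCAT score on the day of surgery".
- **Subgroup.** SAP 6.3 has a two-level split, "ARISCAT score (intermediate [26-44] vs high [45 or higher".

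SAP 6.3 mentions covariates in its title but names none for adjustment. No adjusted supportive analysis is planned and no reason is given. The remark in 6.1.4 on results being easier to understand concerns t-tests of continuous variables.

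**The concern.** When a baseline variable predicts the outcome, leaving it out keeps variation in the error term that could have been removed. It also leaves chance differences in risk between the arms uncorrected. Randomization balances arms within site but not by ARISCAT. If the baseline table shows a visible risk difference and no adjusted analysis was prespecified, any later adjustment is post hoc, whichever way the result falls.

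The primary result also governs how the secondary P-values are read (SAP 6.6), so its precision matters beyond the primary outcome.

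**Working it through.** **Inputs from the documents (SAP 4.6 and 6.5).** PPC rates are 40% under usual care and 25.88% under the bundle, a relative reduction of 35.29%. Severity among patients with a PPC is assumed equal in the two arms: "with no change in the distribution of the severity of complications". Each arm has 375 patients, and the stated power is 93%. Two-sided alpha is 0.05 for planning and 0.0499023 (Z = 1.9608) at the final analysis.

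**Input not in the documents.** R², the share of variance in PPC grade that ARISCAT explains within site among patients scoring 26 or more. I assume 2% to 15%.

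**Step 1: the stated 93%.** It cannot be reproduced exactly, because the split of PPCs across Grades 1 to 4 is not given. With an assumed 70/20/8/2 split, mean severity given a PPC is 1.42 and the mean square is 2.54.

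- Control: mean 0.40 × 1.42 = 0.568; variance 0.40 × 2.54 − 0.568² = 0.693.
- Intervention: mean 0.25884 × 1.42 = 0.368; variance 0.25884 × 2.54 − 0.368² = 0.522.
- Difference 0.200. Standard error 0.0574 under no effect and 0.0569 under the alternative.
- Power = Φ((0.200 − 1.9608 × 0.0574)/0.0569) = 93.9%.

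Other assumed splits give 94.6% (35/35/20/10), 95.2% (25/25/25/25), 95.6% (45/45/8/2) and 96.6% (25/60/12/3). The stated 93% is plausible, and I take it as the starting point.

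**Step 2: gain from model adjustment.** At 93% power the expected Z is 1.960 + 1.476 = 3.436. Adjustment multiplies the standard error by √(1 − R²), so power = Φ(3.436/√(1 − R²) − 1.960), and the equivalent sample size is 750/(1 − R²). This is a large-sample formula.

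| Assumed R² | Standard error smaller by | Power | 750 act like |
|---|---|---|---|
| 2% | 1.0% | 93.5% | 765 |
| 5% | 2.5% | 94.1% | 789 |
| 10% | 5.1% | 95.2% | 833 |
| 15% | 7.8% | 96.1% | 882 |

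**Step 3: what R² might be.** Suppose the two SAP risk groups were equal in size with PPC rates 20 points apart. For any PPC, R² = 0.5 × 0.5 × 0.20²/(0.40 × 0.60) = 4.2%, or about one power point. For grade under the 70/20/8/2 split, with severity unrelated to risk, R² = 0.25 × (0.20 × 1.42)²/0.693 = 2.9%. It would be higher if severity also rises with the score.

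**Step 4: chance imbalance.** The shift in the unadjusted Z from chance ARISCAT imbalance has standard deviation √R². For an adverse imbalance of 1.96 standard deviations, power at the planned effect is Φ((3.436 − 1.96√R² − 1.960)/√(1 − R²)). This gives about 86% at R² = 5% and 82% at 10%. Adjusted power stays near 94% and 95%.

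**Step 5: adding ARISCAT as a second CMH stratum.** I simulated 750 patients at 17 sites, 4,000 runs per setting. PPC rates in the two ARISCAT groups were 0 to 30 points apart, the high-risk share was 30% or 50%, and three severity splits were used. Crossing site with the two groups changed power by −0.7 to +0.7 points. All three splits gained only with a 30-point gap and an even split. Under no effect, the site-only and crossed tests rejected in 5.0% and 5.1% of runs.

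**The case against.** The strongest case against is that nothing is wrong. The analysis follows the randomization, the test holds its level, and chance imbalance is already allowed for in a valid test's error rate. That stands. A reader might infer that the primary comparison is biased or invalid without ARISCAT; the documents do not support this.

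Second, the size is assumed. No R², discrimination figure or PPC rate by score is given. Entry at 26 narrows the range: an upper abdominal incision (15), surgery over 3 hours (23) and age 51 to 80 (3) total only 41, still intermediate. That also stands. At R² = 1%, power would be 93.2%. The upper end of the table, where 750 patients act like 882, should not be read as a known loss.

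Third, a reader might take the gain as free because the score is a baseline value. That is not shown. Duration of surgery contributes up to 23 points, and SAP 5.1 does not say whether the listed score uses expected or actual duration. Actual duration is known only after randomization. The fix must name the version used.

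Fourth, the change is late: the SAP describes 751 participants studied and both interim analyses done. This stands only in part. Protocol Section VI allows the SAP to be completed up to database lock and makes it definitive over the protocol, and keeping the site-only test in the report lets readers see both.

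**Conclusion.** The point holds as an efficiency and robustness improvement. The site-only test is valid, but it omits a risk score required of every participant, with no stated reason and no adjusted analysis. On the planned 93%, the gain is about 0.5 to 3 power points for an assumed R² of 2% to 15%, and about one point near 4% to 5%. Protection against an unlucky risk imbalance is a further benefit.

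These figures rest on the stated 93%, on a large-sample formula and on an R² that the documents do not give. A reader might also expect the gain from adding the two ARISCAT groups to the CMH strata; the simulation shows almost none, because the smaller cells offset it.

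**What to change.** Before database lock and unblinding, amend SAP 6.1.4 and 8.1.1:

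1. Estimate the mean-grade difference and its 95% confidence interval from a linear model of grade (0 to 4) on arm, site and continuous ARISCAT, with robust standard errors. Keep the final significance level of 0.0499023.
2. Define the covariate as the eligibility score fixed before surgery, with expected and not actual duration. Say in SAP 5.1 which duration the listed score uses.
3. Report the site-only CMH row mean score test alongside.
4. Do not cross site with the two ARISCAT groups.

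If results by treatment group have already been seen, keep the CMH test as primary and label the adjusted model supportive.

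The model targets the same kind of quantity that the SAP already reports, a difference in mean grade. The cost is a few lines of SAP text, one more model and a late change to the named primary method, which the SAP should explain. No further patients are needed.

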4.3 Description of Control Group (Usual Care)

The control group follows the usual care at each of the individual sites, without any attempt to standardize the care provided across the institutions. As all sites are academic medical centers or affiliated with academic medical centers, the usual care arm is expected to be representative of current high-quality care for the population.

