4.5.2 Safety Outcomes

The co-primary safety outcomes will be: 1) the proportion of patients with any intraoperative cardiovascular events or pneumothorax; and 2) the proportion with both intraoperative hypoxemia and rescue recruitment maneuvers. Specifically:

- Proportion of participants with intraoperative cardiovascular events (hypotension, bradycardia, tachycardia, arrhythmias, new ST-segment changes, and cardiac arrest) or pneumothorax
- Proportion of participants with both intraoperative hypoxemia and rescue recruitment maneuvers

Other secondary safety outcomes include:

- Length of postoperative oxygen therapy/other respiratory support
- Length of hospital stay
- Proportion of participants with any major extrapulmonary complications (detailed definition is in Appendix I of the protocol; included in Appendix 3 of this document for reference)

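### SAP 6.1.4 leaves site, the randomisation stratum, out of the t-test for continuous variables: valid with respect to site, but it may give up a little precision (optional change)

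*SAP*

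**What the plan says.** SAP 4.1 reports 1:1 allocation and states that "randomization was stratified by site". SAP 6.1.4 then sets three methods:

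- Primary endpoint: row mean score test, stratified by site.
- Binary variables: "A Cochran-Mantel-Haenszel test (with site as a stratification variable) is used for binary variables".
- Continuous variables: "A standard t-test is used for continuous variables and the difference between the groups and the associated 95% confidence will be provided".

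For the third, the SAP gives its reason. The plain difference is held to be easier to understand than one from a site-adjusted model, "which would not be the same as the difference between the two observed means".

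SAP 8.2 sends the safety outcomes to 6.1.4. Two of those in SAP 4.5.2 are continuous: length of hospital stay and "Length of postoperative oxygen therapy/other respiratory support". SAP 7.5 says the intraoperative characteristics of 5.3 will be tested, and these include continuous items such as "duration of mechanical ventilation". SAP 7.5 names no test, so 6.1.4 appears to govern there too.

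Protocol Table 6 had listed a site-stratified van Elteren test for continuous variables. Protocol VI makes the final SAP definitive where the two differ.

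**The concern.** When randomisation is stratified, the analysis normally includes the stratum, so that variation between strata is removed from the error term. Here that is done for two of the three kinds of outcome.

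Site could plausibly matter for the third. Usual care was left to each hospital "without any attempt to standardize the care provided across the institutions", and the practice survey in Protocol Table 4 shows wide spread: consistent early ambulation reached more than 80% of patients at 50% of the centers and fewer than 20% at 14% of them. Length of stay and ventilator settings may vary in the same way.

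The stated reason for leaving site out is also thin. The adjusted and raw differences are indeed not identical, but under 1:1 allocation within site they should be close. SAP 6.1.3 already summarises continuous variables by means and SDs, so the raw means can stand beside an adjusted difference.

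At stake is the width of some secondary confidence intervals. Bias is not at issue.

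**Working it through.** The plan gives no power, SD, ICC or interval width for any continuous outcome, so there is no figure of its own to reproduce on this point.

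**Inputs from the documents.** "We studied 751 adult participants" (SAP 4.1); 1:1 allocation (SAP 4.1); 17 sites (Protocol IV); about 6% lost after randomisation (SAP 4.6), so 750 / 0.94 ≈ 798 randomised and 798 − 751 = 47 not analysed; a half-day difference in length of stay counted as clinically important (Protocol V).

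**Assumed.** Site ICC 0 to 0.10; SD 5 days for length of stay (3 and 8 also tried); blocks of 4 or no blocking; 5 patients per attending; normal outcomes.

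**1. Blocked allocation.** The t-test keeps between-site variance in its error term and the site model removes it. With S equal sites, the ratio of interval widths (t-test / site-adjusted) is √(1 + ICC(1 − 1/S)/(1 − ICC)). With S = 17:

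- ICC 0.02: √(1 + 0.02 × 0.9412/0.98) = √1.0192 = 1.010
- ICC 0.05: √(1 + 0.05 × 0.9412/0.95) = √1.0495 = 1.024
- ICC 0.10: √(1 + 0.10 × 0.9412/0.90) = √1.1046 = 1.051

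The SD cancels. Using 18 sites instead of 17 changes nothing before the fourth decimal.

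**2. Unblocked allocation.** Chance imbalance within sites costs the adjusted model information. The ratio is multiplied by about √((751 − 17)/(751 − 1)) = √(734/750) = 0.989, giving 0.989, 0.999, 1.013 and 1.040 at ICC 0, 0.02, 0.05 and 0.10. Break-even is near ICC 0.02.

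**3. Simulation.** 798 randomised in 17 unequal sites, 47 removed at random, pooled t-test against least squares with site fixed effects. Excess width of the t-test interval:

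| Site ICC | Blocked, formula | Blocked, simulated | Unblocked, formula | Unblocked, simulated |
|---|---|---|---|---|
| 0 | 0% | about 0% | −1.1% | −1.1% |
| 0.02 | 1.0% | 0.8% | −0.1% | about 0% |
| 0.05 | 2.4% | 2.3% | 1.3% | 1.3% |
| 0.10 | 5.1% | 4.9% | 4.0% | 3.8–4.0% |

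**4. In days.** At SD 5 with 375.5 per arm, the t-test half-width is 1.96 × 5 × √(2/375.5) ≈ 0.72 day. At ICC 0.10, blocked, adjustment gives 0.72/1.051 ≈ 0.68 day.

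**5. Raw against adjusted difference.** At SD 5 and ICC 0 to 0.20, the gap between the two estimates has an SD of 0.02–0.05 day if blocked and 0.06–0.17 day if unblocked. Both are small beside 0.72 day.

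**6. Power for a half-day difference (blocked, SD 5).** At ICC 0.02 / 0.05 / 0.10: t-test 27.5 / 27.4 / 25.9%, site-adjusted 28.1 / 29.6 / 29.2% (Monte Carlo SE up to about 0.9 points). Up to ICC 0.10 the gain is 0–4 points at SD 3 and 0–3 points at SD 8.

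**7. Type I error, site effects only (blocked).** At ICC 0 / 0.05 / 0.10: t-test 5.2 / 4.3 / 4.3%, site-adjusted 5.2 / 4.7 / 5.4% (SE about 0.3). The t-test is not inflated; it is slightly conservative when site matters.

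**8. Adding clustering by attending.** Protocol V randomises anesthesiologists so that each cares for patients of one arm only. At site ICC 0.10, blocked, with within-attending correlation 0.01 / 0.02 / 0.05, type I error is 4.5 / 5.2 / 6.6% (t-test) and 5.5 / 6.3 / 8.1% (site-adjusted), differences of 1.0 / 1.1 / 1.5 points.

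**The case against.** The case for leaving the SAP alone is fair, and most of it stands.

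- *The choice is disclosed, reasoned and permitted.* This stands. A reader might infer that the SAP breaches the protocol by dropping the van Elteren test. It does not, because the protocol gives the SAP precedence. The remaining point is that printing raw means meets the readability aim equally well.
- *Nothing depends on it.* This largely stands. No continuous variable is the primary or a co-primary safety outcome. SAP 6.6 says confidence limits are not for hypothesis testing, and secondary P-values do not indicate significance if the primary fails.
- *The gain is barely visible.* This stands at the low end. To one decimal, 0.72 and 0.68 day both print as 0.7, and SAP 6.1.2 reports derived variables to one decimal.
- *The size, and even the sign, depends on unknowns.* This stands. The result must be stated separately for blocked and unblocked allocation.
- *If outcomes cluster by attending, adjustment makes the error rate worse.* This is the strongest argument. A reader might infer that the t-test interval is simply wider than necessary. The documents do not support that without qualification, because attendings were randomised to arms and an interval that ignores them may already be too narrow. Still, slack that arises by accident from ignoring site is no remedy for that clustering, which would need its own treatment.

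**Conclusion.** The omission is real and its consequence is small. At assumed site ICC 0.02 / 0.05 / 0.10, the t-test interval is about 1 / 2 / 5% wider than a site-adjusted one under blocked allocation, and about 0 / 1 / 4% wider under unblocked allocation. At ICC 0 nothing is lost, and unblocked the t-test is about 1% narrower.

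A reader might infer that ignoring the stratum invalidates the test or inflates false positives. It does neither with respect to site: the difference in means stays unbiased, and under blocked allocation the test errs on the conservative side. That statement covers site only and says nothing about clustering by attending.

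The figures rest on assumed ICCs, block size and normal outcomes; the day and power figures also rest on the assumed SD. This is an optional improvement, held with medium confidence.

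**What to change.** In SAP 6.1.4, take the mean difference, 95% CI and P-value for continuous variables from a linear model with treatment and site as fixed effects, and print raw means (SD) by arm beside them. The SAP was written after enrolment and both interim analyses. If treatment-group results have already been seen, keep the t-test as planned and report the site-adjusted model as a labelled sensitivity analysis.

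The cost is one sentence in the SAP and one model call, with no new data. There are two downsides: an interval about 1% wider if allocation was unblocked and site explains nothing, and the loss of roughly 0–1.5 points of conservative slack in type I error if outcomes cluster by attending anesthesiologist, which neither method handles.
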